4.2 Hydroxychloroquine Group

Participants assigned to the hydroxychloroquine arm will receive hydroxychloroquine sulfate 400 mg enterally twice daily for the first two doses and then 200 mg twice daily for the subsequent eight doses ("Days 2 – 5"). This dosing regimen is a total of 10 doses over 5 days with an 800 mg load in the first 24 hours divided into two doses followed by 400 mg daily divided into two doses over the following 4 days. Medication dose packs containing all 10 doses will be provided at randomization by the investigational pharmacy.

Hydroxychloroquine is available in 200 mg oral tablets of hydroxychloroquine sulfate. Common hydroxychloroquine dosing for treatment of uncomplicated malaria is 800 mg followed by 400 mg at 6 hours, 24 hours, and 48 hours. Common initial dosing for rheumatoid arthritis is 400 mg to 600 mg daily. For this COVID-19 trial, we selected a dose of hydroxychloroquine (400 mg twice daily for the first two doses followed by 200 mg twice daily for next 8 doses) based on similar doses being well tolerated in the treatment of other conditions and *in vitro* studies suggesting that SARS-CoV-2 inhibition is achieved by a dose of 800 mg on the first day followed by 400 mg for the following 4 days.⁵ This dose and duration is comparable to the dose and duration being administered empirically to patients with COVID-19 as a part of clinical care during the current epidemic.

4.3 Control Group

Participants randomized to the control group will receive matching placebo enterally twice daily matching the dosing regimen described above for hydroxychloroquine. Medication dose packs containing all 10 doses will be provided at randomization by the Investigational Pharmacy. The placebo pills will be as similar as possible to the hydroxychloroquine pills to ensure blinding.

4.4 Co-Interventions

This trial will control the use of hydroxychloroquine vs placebo during the 5-day intervention period. Enrolled participants will not receive open-label hydroxychloroquine or chloroquine during the 5-day intervention period. All other treatment decisions will be made by treating clinicians without influence from the protocol. Administration of other antiviral medications (“rescue therapy”) will be allowed. The decision to administer other antiviral medications will be made by treating clinicians and will be recorded in the case report form. The decision to administer immunomodulating medications, including corticosteroids, will be made by treating clinicians and will be recorded in the case report form.

4.5 On-Study Monitoring

All patients enrolled in the study will be initially hospitalized and will therefore receive monitoring as a part of routine clinical care, including monitoring by their physicians, nurses, respiratory therapists, and ancillary staff.

In addition to routine clinical monitoring, enrolled patients will have an assessment of the QTc with an electrocardiogram (EKG) or rhythm strip performed 24-48 hours after administration of the first study medication. If an EKG or rhythm strip has been performed as a part of clinical care during this window, study personnel will assess the QTc on these clinically performed tracings. If an EKG or rhythm strip has not been performed as a part of clinical care during this window, an EKG or rhythm strip will be ordered and performed as a part of study procedures. This QTc will be used to monitor patient safety and inform stopping of the study drug as described below. If a patient is discharged from the hospital before the QTc is evaluated at 24-48 hours, the study drug may be continued after discharge without this assessment.

Between randomization and Day 5, study personnel will review the electronic health record daily for potential medication interactions with hydroxychloroquine (see Appendix B). If a medication that is considered to be contraindicated with hydroxychloroquine is discovered, treating clinicians will be contacted to discuss if stopping study drug is appropriate or if the medication in question can be stopped or substituted. If a medication with a potential interaction with hydroxychloroquine is identified, study

personnel will contact treating clinicians to ensure they are aware of the potential interaction. Treating clinicians will determine whether an alternative medication would be appropriate or whether the risk-benefit ratio favors continuing the medication with the known potential interaction. If a patient is started on a medication listed in Appendix B that potentially prolongs the QTc, study personnel will recommend to treating clinicians use of continuous cardiac monitoring when available during the study drug treatment period.

In addition to manual monitoring by study personnel for medication interactions, many electronic health records contain tools within the electronic order entry system to automatically screen for medication interactions with hydroxychloroquine and notify ordering providers of the potential interaction at the time of order entry.

4.6 Criteria for Stopping Study Drug

Administration of the blinded study drug may be stopped temporarily or permanently for (a) adverse events, (b) results of on-study monitoring, (c) clinical deterioration, or (d) evidence of an alternative cause to the patient's symptoms.

If a patient experiences an adverse event that the patient (or legally authorized representative), treating clinicians, or investigators feel merits temporarily or permanently stopping the study drug, the study drug will be stopped. The explanation for stopping the study drug will be recorded in the case report form, and the adverse event will be recorded and reported according to the adverse event guidelines below. If the adverse event resolves to the extent that the patient (or legally authorized representative), treating clinicians, and investigators feel that resuming the study drug is appropriate, the study drug will be resumed, and this information will be recorded in the case report form.

If a QTc assessed after randomization is >500 ms, the study drug will be discontinued for 24 hours and a repeat EKG will be performed daily until either the QTc is less than 500 ms, at which time study drug is resumed until 5 days after randomization with daily QTc assessments, or until 5 days after randomization is reached without resumption of study drug. Both the value for the QTc and the decision to continue or stop the study drug will be recorded in the case report form. If the QTc in hospitalized patients cannot be assessed at 24-48 hours, study drug will be discontinued until the QTc can be assessed. If the daily on-study monitoring by study personnel for medication interactions indicates a potential interaction with a medication that treating clinicians feel is required for the optimal treatment of the patient and with which treating clinicians and the investigator feel it would be unsafe to administer hydroxychloroquine (including but not limited to: amiodarone; cimetidine; chloroquine; dofetilide; phenobarbital; phenytoin; sotalol), the study drug will be stopped and the reason will be recorded in the case report form.

Patients on study may experience clinical deterioration due to their illness. Clinical deterioration will be defined as a decrease of 1 point or more on the ordinal scale for the primary outcome (e.g., patient transitions from "hospitalized on supplemental oxygen" to "hospitalized on non-invasive ventilation or high flow nasal cannula"). Patients who experience clinical deterioration in either group may be administered other antivirals or immunomodulators as "rescue therapy". For patients who experience clinical deterioration for which treating clinicians feel optimal care would be to stop the study drug, unblind group assignment, and administer hydroxychloroquine to patients in the placebo group, the study drug will be stopped, the site investigator will contact the coordinating center to receive the unblinded

study group assignment, and any additional treatment will be deferred to treating clinicians. In this situation, the following data will be recorded in the case report form: the criteria met for clinical deterioration; the reason for stopping study drug and unblinding; use of hydroxychloroquine, other antivirals, and immunomodulators; and study outcomes. Crossovers from placebo to open-label hydroxychloroquine will be recorded and reported to the DSMB at DSMB reviews and interim analyses.

Before implementation of protocol version 2.0, patients could be enrolled with a pending SARS-CoV-2 test result if clinical criteria were present suggesting a high likelihood of COVID-19. In these patients, if SARS-CoV-2 results returned negative and the clinical team identified a likely alternative cause of the patient's clinical syndrome, the clinical team could elect to stop administration of the study drug. If the study drug was stopped for this reason, the timing and reason for study drug discontinuation was recorded. After implementation of protocol version 2.0, only patients with laboratory-confirmed SARS-CoV-2 infection are eligible.

5. OUTCOMES

5.1 Primary Outcome

COVID Ordinal Outcomes Scale on Study Day 15:

1. Death
2. Hospitalized on invasive mechanical ventilation or ECMO
3. Hospitalized on non-invasive ventilation or high flow nasal cannula
4. Hospitalized on supplemental oxygen
5. Hospitalized not on supplemental oxygen
6. Not hospitalized with limitation in activity
7. Not hospitalized without limitation in activity

5.2 Secondary Outcomes

- Time to recovery, defined as time to reaching level 5, 6, or 7 on the COVID Outcomes Scale, which is the time to the earlier of final liberation from supplemental oxygen or hospital discharge
- All-location, all-cause 14-day mortality (assessed on Study Day 15)
- All-location, all-cause 28-day mortality (assessed on Study Day 29)
- COVID Ordinal Outcomes Scale on Study Day 3
- COVID Ordinal Outcomes Scale on Study Day 8
- COVID Ordinal Outcomes Scale on Study Day 29
- Composite of death or receipt of ECMO through Day 28
- Oxygen-free days through Day 28
- Ventilator-free days through Day 28
- Vasopressor-free days through Day 28
- ICU-free days through Day 28
- Hospital-free days through Day 28

5.3 Safety outcomes

- Seizure
- Atrial or ventricular arrhythmia
- Cardiac arrest

- Elevation in aspartate aminotransferase or alanine aminotransferase to twice the local upper limit of normal
- Acute pancreatitis
- Acute kidney injury
- Receipt of renal replacement therapy
- Symptomatic hypoglycemia
- Neutropenia, lymphopenia, anemia, or thrombocytopenia
- Severe dermatologic reaction

5.4 Rationale for Primary Outcome

COVID-19 has a broad spectrum of clinical severity. Even among hospitalized patients, most recover without experiencing critical illness.³⁰ Designing a trial with statistical power to detect a meaningful difference in ICU-free days or mortality might require an unfeasibly large sample size and could miss significant morbidity experienced by the majority of hospitalized patients. Since the majority of morbidity from COVID-19 relates to hypoxemia, the fact that this outcome is tied to degree of hypoxemic respiratory failure increases its face validity and relevance. For similar reasons, previous trials of severe influenza have employed a similar ordinal outcome.³¹ This ordinal scale has been selected as an outcome in multiple ongoing COVID-19 trials and is a preferred outcome by the World Health Organization Research and Development Blueprint for COVID-19.³² Use of this standardized outcome will increase the potential to compare the results of this trial with other trials and perform meta-analyses.

6. DATA COLLECTION

Given the infectious risk from COVID-19 and potential shortages of personal protective equipment (PPE), we will minimize face-to-face contact between patients and non-clinical staff. Additionally, minimizing research activities and conducting the trial in a pragmatic manner will increase the ability to complete the trial in the face of strained clinical and research resources during the COVID-19 pandemic. We will emphasize data that can be collected from the electronic health record, radiographs obtained as part of routine clinical care, and assessments that can be completed over the telephone as needed.

Biological specimens will not be collected as part of this trial. To further elucidate the pathophysiology of COVID-19 and the effects of hydroxychloroquine, we encourage ancillary studies and co-enrollment in observational studies that collect biological specimens and more detailed data.

6.1 Baseline Variable Collection

- Presence or absence of inclusion and exclusion criteria
- Date and time of randomization
- Date of symptom onset
- Admission data: date and time of presentation, origin (home, skilled nursing facility, rehabilitation/LTACH, nursing home, outside hospital, outside ICU), location at enrollment (ED, hospital ward, ICU)
- Demographics (age, sex, race, ethnicity, height, weight)

- Comorbidities: AIDS, Leukemia, Malignant Lymphoma, Hemiplegia, Cerebrovascular Disease, A prior myocardial infarction, Congestive Heart Failure, Peripheral vascular disease, Dementia, COPD, Connective tissue disease, Peptic ulcer disease, History of hypertension, HIV positive (without AIDS), Alcoholism, Coronary artery disease, Rapidly fatal disease, Solid tumor, Liver disease, Diabetes mellitus, Moderate to severe kidney disease
- Acute signs and symptoms: altered mental status, acute hypoxemic respiratory failure, liver function tests, renal function, coagulation studies, chest imaging results
- Sequential Organ Failure Assessment (SOFA)³³ at enrollment
- Chronic use of medication: corticosteroids, ACE inhibitors, angiotensin receptor blockers, non-steroids anti-inflammatory drugs, other
- Receipt of open label antivirals between hospital presentation and enrollment: chloroquine, hydroxychloroquine, remdesivir, lopinavir/ritonavir, other
- Receipt of open label immunomodulators between hospital presentation and enrollment: corticosteroids, tocilizumab, sarilumab, interferon β , other
- Receipt of convalescent plasma between hospital presentation and enrollment
- Receipt of azithromycin between hospital presentation and enrollment
- Receipt of invasive mechanical ventilation, non-invasive ventilation, high-flow nasal cannula, vasopressors, and oxygen therapy at enrollment
- Highest fraction of inspired oxygen, lowest arterial oxygen saturation, highest respiratory rate, lowest systolic blood pressure, highest heart rate in the 12 hours prior to enrollment
- Diagnosis of Acute Respiratory Distress Syndrome (ARDS) by Berlin Criteria³³ at enrollment
- COVID Ordinal Outcomes Scale at enrollment

6.2 Assessments between Hospital Presentation and Hospital Discharge

- Specimen type, date, and result of SARS-CoV-2 testing conducted clinically
- Specimen type, date, and result of viral testing conducted clinically
- Specimen type, date, and result of bacterial testing conducted clinically
- Date and time of study drug administration and reason for missed doses
- COVID Ordinal Outcomes Scale on Days 2, 3, 4, 5, 8, 15, and 29
- SOFA on Day 3
- S/F ratio on Day 3
- Receipt of open label antivirals between randomization and hospital discharge: chloroquine, hydroxychloroquine, remdesivir, lopinavir/ritonavir, other
- Receipt of open label immunomodulators between randomization and hospital discharge: corticosteroids, tocilizumab, sarilumab, interferon β , other
- Receipt of convalescent plasma between hospital presentation and enrollment
- Receipt of azithromycin and other antibiotics between randomization and Day 8
- Clinically diagnosed deep vein thrombosis (DVT) or pulmonary embolism (PE) between hospital presentation and hospital discharge.
- Date and time of first receipt of supplemental oxygen (if applicable)
- Date and time of final receipt of supplemental oxygen (if applicable)
- Date and time of first receipt of high flow nasal cannula (if applicable)

- Date and time of final receipt of high flow nasal cannula (if applicable)
- Date and time of first receipt of non-invasive ventilation (if applicable)
- Date and time of final receipt of non-invasive ventilation (if applicable)
- Date and time of first receipt of invasive mechanical ventilation (if applicable)
- Date and time of final receipt of invasive mechanical ventilation (if applicable)
- Date and time of first receipt of extracorporeal membrane oxygenation (if applicable)
- Date and time of final receipt of extracorporeal membrane oxygenation (if applicable)
- Date and time of first receipt of vasopressors (if applicable)
- Date and time of final receipt of vasopressor (if applicable)
- Date and time of first meeting the Berlin Diagnostic Criteria for ARDS³³ (if applicable)
- Date and time of first ICU admission (if applicable)
- Date and time of final ICU discharge (if applicable)
- Date and time of hospital discharge (if applicable)
- Date of death (if applicable)
- Safety Outcomes: seizure, atrial or ventricular arrhythmia, cardiomyopathy, cardiac arrest, aspartate aminotransferase or alanine aminotransferase levels that are greater than twice the local upper limit of normal, acute pancreatitis (defined by a clinically obtained lipase level above the local upper limit of normal), stage II or greater acute kidney injury according to KDIGO criteria³⁴, receipt of new renal replacement therapy, symptomatic hypoglycemia, neutropenia, lymphopenia, anemia, thrombocytopenia, or severe dermatologic reaction (e.g., Steven's Johnson Syndrome)
- Patient destination at discharge

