9.1.1 Potential risks of receiving hydroxychloroquine

Potential risks of receiving hydroxychloroquine can be classified based on their severity as Major or Minor. Major potential risks of receiving hydroxychloroquine include:

- 1) Neurological System
 - a) Seizure – Hydroxychloroquine can lower the seizure threshold and co-administration of hydroxychloroquine with other medications known to lower the seizure threshold has been reported to increase the risk of seizures. This trial protocol excludes patients with a seizure disorder.
 - b) Psychosis – A small number of case reports describe psychosis in patients on long-term treatment with hydroxychloroquine,³⁹ but has not been described with short-term treatment.
 - c) Suicidal behavior - Suicidal behavior has been rarely reported in patients on long-term treatment with hydroxychloroquine for rheumatologic disorders,⁴⁰ but not with short-term therapy.
- 2) Circulatory system
 - a) Cardiac arrhythmias
 - i) Ventricular arrhythmias and torsades de pointes – Hydroxychloroquine can prolong the QT interval and ventricular arrhythmias and torsades de points have been reported in patients taking hydroxychloroquine. This trial protocol excludes patients with a prolonged QTc on baseline EKG and history of prolonged QTc syndromes, assesses the QTc after receipt of study drug, monitors daily for co-administration of medications that prolong the QTc and specifies criteria for stopping the study drug based on prolonged QTc.
 - ii) Cardiomyopathy, sick sinus syndrome, atrioventricular block, or bundle branch block – Cardiomyopathy and conduction system disease have rarely been reported among patients on long-term hydroxychloroquine,⁴¹ but have not been reported among patients receiving less than 3 months of therapy.
- 3) Digestive system
 - a) Liver injury – Fulminant hepatic failure has been reported in at least two cases from long-term administration of hydroxychloroquine.⁴² Porphyrria cutanea tarda appears to be a risk factor for liver injury from hydroxychloroquine. This trial protocol excludes patients with porphyria cutanea tarda.
 - b) Increased cyclosporine or digoxin levels – hydroxychloroquine can increase levels of cyclosporine or digoxin for patients being co-administered these medications. This trial protocol monitors daily for receipt of medications that interact with hydroxychloroquine and notifies treating clinicians about potential medication interactions.
- 4) Endocrine system

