Intensive care unit-free days (ICU-free days) to day 28 was defined as the number of whole calendar days alive and not admitted to an intensive care unit from 00:00 on the day of randomization through Study Day 29. Patients who died before Study Day 29 received a value of 0. If a patient survived to the first of discharge or Study Day 29 and was never admitted to an ICU, the number of ICU-free days was 28. If a patient was admitted to an ICU and survived to the first of discharge or Study Day 28, the number of ICU-free days was calculated as 28 minus the number of calendar days from the first ICU admission to final ICU discharge. Days on which the patient was not admitted to an ICU that occurred between days on which the patient was admitted to an ICU did not count towards the number of ICU-free days. Data on ICU use was censored at hospital discharge and the last observed status was carried forward (“in-hospital outcome”). That is, the analysis assumed that a patient who was discharged from the index hospitalization was not readmitted to an ICU between hospital discharge and Study Day 29.

Hospital-free days to Day 28

Hospital-free days to Day 28 was defined as the number of whole calendar days on which the patient was alive and not in the hospital from 00:00 on the day of randomization through Study Day 29. Patients who died before Study Day 29 received a value of 0. If a patient remained in the hospital during the index hospitalization through Study Day 29, the number of hospital-free days was 0. For patients

discharged from the index hospitalization prior to Study Day 28, the number of hospital-free days was calculated as 28 minus the duration of the index hospitalization in calendar days. Information readmissions occurring after discharge from the index hospitalization did not contribute to the calculation of the hospital-free days outcome.

Definition of Safety Outcomes (“all-location outcomes”)

1. Seizure – Between randomization and Study Day 29, as documented by treating clinicians in the electronic health record or reported by patient or surrogate on follow up telephone call.
2. Atrial arrhythmia - Between randomization and Study Day 29, as documented in the electronic health record or reported by patient or surrogate on follow up telephone call.

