3. Ventricular arrhythmia - ventricular tachyarrhythmia (ventricular fibrillation or ventricular tachycardia) treated with a medication or electrical cardioversion or debrillation between randomization and Study Day 29, as documented in the electronic health record or reported by patient or surrogate on follow up telephone call.
4. Cardiac arrest - Between randomization and Study Day 29, as documented in the electronic health record or reported by patient or surrogate on follow up telephone call. Does not include expected cardiac arrests occurring as a part of the dying process for patients on comfort measures.
5. Elevation in aspartate or alanine aminotransferase to twice the upper limit of normal – Between randomization and Study Day 29, as documented in the electronic health record or reported by patient or surrogate on follow up telephone call.
6. Acute Pancreatitis – Clinically-obtained lipase level above the local upper limit of normal between randomization and day 29.
7. Acute Kidney Injury – Stage II or greater acute kidney injury by Kidney Disease Improving Global Outcomes (KDIGO) Criteria between randomization and day 29, defined as any of the following:
 - a. Creatinine at least 2.0 times the baseline value
 - b. Increase in serum creatinine above 4.0 mg/dl
 - c. Urine output less than 0.5 ml/kg/h for at least 12 hours
 - d. Initiation of new renal replacement therapy
8. Receipt of renal replacement therapy – Between randomization and Study Day 29, as documented by treating clinicians in the electronic health record or reported by patient or surrogate on follow up telephone call.
9. Symptomatic hypoglycemia – Between randomization and Study Day 29, as documented by treating clinicians in the electronic health record or reported by patient or surrogate on follow up telephone call.
10. Neutropenia – Clinically-obtained absolute neutrophil count < 1000 (cells/mm³) between randomization and Study Day 29
11. Lymphopenia – Clinically obtained absolute lymphocyte count < 1000 (cells/mm³) between randomization and Study Day 29.
12. Anemia – Clinically-obtained hemoglobin < 12.0 g/dL between randomization and Study Day 29.

13. Thrombocytopenia – Clinically-obtained platelet count < 50 (cell/mm³; in thousands) between randomization and Study Day 29.

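### The SAP's atrial arrhythmia outcome has no new-onset condition and protocol 6.1 lists no baseline arrhythmia status, so pre-existing cases can count as events and pull that row's odds ratio toward 1

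*Protocol*

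**What the plan says.** **Outcome.** Protocol 5.3 has one combined item, "Atrial or ventricular arrhythmia", and protocol 6.2 repeats it within "Safety Outcomes: seizure, atrial or ventricular arrhythmia, cardiomyopathy, cardiac arrest". SAP Appendix A splits it into two rows. The operative definition is in SAP Appendix B, Definition of Safety Outcomes. Item 2 reads "Atrial arrhythmia - Between randomization and Study Day 29, as documented in the electronic health record", or by patient or surrogate report at a follow-up call. It sets no condition on new onset, treatment or severity. Item 3 is narrower: a ventricular event must be "ventricular tachyarrhythmia (ventricular fibrillation or ventricular tachycardia) treated with a medication or electrical cardioversion" or defibrillation.

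**Baseline.** Protocol 6.1 lists 21 comorbidities. The cardiac and vascular entries include "A prior myocardial infarction, Congestive Heart Failure, Peripheral vascular disease, Dementia, COPD", hypertension and coronary artery disease, but no atrial fibrillation, flutter or other arrhythmia. The physiological variables include "lowest systolic blood pressure, highest heart rate in the 12 hours prior to enrollment", but not rhythm. Protocol Appendix A schedules an EKG before enrollment; the only use the protocol names for it is the QTc exclusion.

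**Eligibility.** Atrial fibrillation is not an exclusion. Exclusion 11 removes some of these patients, namely those with recent or non-substitutable amiodarone, dofetilide or sotalol.

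**Analysis.** SAP 7.5 analyses safety outcomes by logistic regression without covariates.

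**The concern.** Chronic atrial fibrillation tends to be documented throughout a hospital stay. Read literally, item 2 is met on Study Day 1 by such a patient, whatever the treatment. Those patients add events to both arms that the drug cannot have caused.

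In a harm comparison, attenuation leans toward false reassurance. The table by arm also matters more than usual here: under protocol 11.2 and Appendix C.3, arrhythmia is exempt from adverse event reporting unless the investigator judges it related or of uncertain relationship. Finally, an item that can be read as any arrhythmia or as new arrhythmia only may be applied differently across sites.

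**Working it through.** **Text check.** The plan deals with baseline status for several other outcomes:

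- The ECMO composite does not let a patient already on ECMO at randomization qualify by staying on it.
- Acute kidney injury uses creatinine relative to baseline and requires any dialysis to be new.
- Protocol 6.2 asks for "receipt of new renal replacement therapy", although the SAP's own renal replacement item omits the word new.

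Item 2 has no comparable condition.

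**Inputs.** From the documents: up to 510 patients randomized 1:1, so 255 per arm. They give no atrial fibrillation prevalence, atrial event rate, or alpha or power target for this outcome, so there is no planned figure to reproduce. Assumed: two-sided alpha 0.05; new-onset risk p of 5% on placebo and 10% on hydroxychloroquine; prevalence b of 5%, 10% or 15% in each arm; every prevalent case counted.

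**Formulas.**

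- Observed risk = b + (1 − b) × p.
- Power = Φ[(d − 1.96 × SE0) / SE1], where d is the risk difference, SE0 = √[p̄(1 − p̄) × 2/n] and SE1 = √{[p0(1 − p0) + p1(1 − p1)]/n}.

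**Worked case, b = 10%.**

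- Placebo: 0.10 + 0.90 × 0.05 = 0.145. Hydroxychloroquine: 0.10 + 0.90 × 0.10 = 0.190.
- OR = (0.190/0.810) / (0.145/0.855) = 1.38.
- d = 0.045, SE0 = 0.0331, SE1 = 0.0330, so power = Φ(−0.60) = 27%.
- Prevalent cases per arm: 255 × 0.10 = 25.5. New-onset placebo events: 255 × 0.90 × 0.05 = 11.5.

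| Prevalence | Observed risks | Risk difference | OR | Power | Power, new onset only, n = 255(1 − b) |
|---|---|---|---|---|---|
| 0 | 5.0% v 10.0% | 5.0 points | 2.11 | 57% | 57% |
| 5% | 9.75% v 14.5% | 4.75 | 1.57 | 38% | 55% |
| 10% | 14.5% v 19.0% | 4.5 | 1.38 | 27% | 53% |
| 15% | 19.25% v 23.5% | 4.25 | 1.29 | 21% | 51% |

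Under the new-onset definition the OR stays at 2.11.

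**Other assumed rates, at prevalence 0, 5% and 10%.** New onset 3% v 6%: power 37%, 20%, 14%. New onset 8% v 16%: power 80%, 64%, 52%. The direction is the same throughout.

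**If only half the prevalent cases are counted** (b = 10%, 5% v 10%): risks are 0.05 + 0.90 × 0.05 = 0.095 and 0.05 + 0.90 × 0.10 = 0.140, so OR = (0.140/0.860) / (0.095/0.905) = 1.55. The attenuation is smaller but still present.

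**The case against.** **The drug's main cardiac risk is elsewhere.** This stands. The statement "This trial protocol excludes patients with a prolonged QTc on baseline EKG" in protocol 9.1.1 belongs to the paragraph on ventricular arrhythmia and torsades, and atrial fibrillation is not among the circulatory risks named there. The SAP analyses treated ventricular events and cardiac arrest in their own rows and reports on-study QTc. A reader might infer that pre-existing atrial fibrillation hides that signal. Under the SAP it does not, though it would reach ventricular events if the combined protocol 5.3 item were reported.

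**The data may exist.** This also stands. The case report form is not in the documents, and the protocol's lists are not exhaustive: SAP Appendix C includes troponin and electrolytes that protocol 6.2 does not name. A reader might infer that baseline status is never captured, or that the analysis cannot be rescued. The documents show only that it is not listed, and the chart and EKG can be abstracted.

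**Item 2 can be read as new events only.** That is possible. It replaces certain counting with uncertain counting, which is itself a reason to define the item.

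**An any-occurrence rule may be intended.** The anemia and lymphopenia rows also count any qualifying value in the window. That weakens the inference of oversight, but it leaves the attenuation in place.

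**Other safeguards exist, and the comparison is weak anyway.** Related or uncertain events and those causing permanent discontinuation are reportable, and the DSMB reviews outcomes. Power is only 57% even with no prevalent cases, and the absolute excess shrinks only from 5.0 to 4.25 points at 15% prevalence. These limit the importance of the point. They do not correct the odds ratio or the inflated event rate.

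**Conclusion.** The point holds for the SAP's atrial arrhythmia row. As worded, item 2 admits pre-existing cases in both arms, the variables listed in protocol 6.1 cannot separate them, and the unadjusted model does not correct for them. The consequences are an odds ratio drawn toward 1, an inflated event rate and possible inconsistency between sites.

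A reader might infer a bias toward one arm. Randomization balances prevalent disease in expectation, so this is dilution and does not tilt the comparison either way.

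The direction is firm under the literal reading; the size is not. OR 2.11 falling to between 1.57 and 1.29, and power from 57% to between 38% and 21%, rest on assumed prevalence of 5% to 15%, assumed new onset of 5% v 10%, and every prevalent case being counted. This is a cheap improvement to one safety row and does not bear on the primary analysis.

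**What to change.** 1. In protocol 6.1, add history of atrial arrhythmia and the rhythm on the pre-enrollment EKG already scheduled. For patients already enrolled, take both from the chart before database lock, while staff remain blinded.
2. In SAP Appendix B item 2 and Appendix A, make the analysed event an atrial arrhythmia first documented after randomization in a patient with none in the history or on the baseline EKG.
3. Add a descriptive row, by arm, for patients with baseline or prior atrial arrhythmia, so that recurrences stay visible.
4. State that the combined protocol 5.3 item is reported as its two components, as SAP Appendix A already has it.

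**Cost.** Two chart-derived fields and one revised definition, with no new patient contact. The denominator shrinks (about 230 per arm at 10% prevalence), and recurrent events in patients with a prior history leave the analysed comparison and appear only in the descriptive row.
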